### Protocol Version 3.0 (25 Feb 2022)

This amendment (Version 3.0) updates and supersedes Protocol THE630-21-101 Version 2.0 dated 07 October 2021, as follows:

- Sections 2.1.1, 3.1, 3.2, 4.1, 9.4, Figure 2: Due to the evolving GIST investigational landscape, the phase 2 study design has been amended to remove original expansion Cohort 3, which was to enroll patients with unresectable or metastatic GIST who had progressed on or were intolerable to imatinib and ripretinib.
- Section 4.1, Figure 2: The entry criteria for expansion Cohort 2 has been amended to remove the exclusion of prior ripretinib, in line with the parallel amendment to remove original expansion Cohort 3.
- Section 6.3.1, Table 1 footnote 1: To clarify a discrepancy with Table 1 footnote 13 and Section 7.3.8, language indicating ECHO/MUGA scan should be performed on C1D1 if not performed with 7 days prior was removed.
- Section 5.9.2 was amended to include 12 mg capsules in the list of supplied capsule strengths of THE-630 drug product.
- Section 8.2 was amended to explicitly clarify that SAEs observed by the investigator or reported by the patient that occur after 30 days after the last dose of study drug through the end of the survival follow-up period should be reported if there is a reasonable possibility that the event may have been caused by THE-630.
- Section 8.2.2 was amended to clarify that the Investigator may change opinion of causality in light of follow-up information.
- Section 8.2.6 was amended to clarify that reports of pregnancy will be submitted on the study Pregnancy Notification Form rather than in the clinical trial database (eCRF) and that pregnancy outcomes should be reported on the Pregnancy Outcome Form.
- Section 8.2.7 was amended to clarify that situations of abuse, misuse, overdose and medication error will be submitted using the study Special Situations Report Form.
- Section 8.3 was amended with minor clarifications on instructions for SAE reporting.
- Section 11: References were updated to correct identified inconsistencies with citations in the body of the protocol.
- Correction was made to fix minor typos throughout.
- Synopsis was updated to reflect all applicable changes.

## Protocol Version 2.0 (07 Oct 2021)

This amendment (Version 2.0) updates and supersedes Protocol THE630-21-101 Version 1.0 dated 02 Sep 2021, as follows:

- Exclusion criterion #12 was modified to align more closely with FDA guidance ([Cancer Clinical Trial Eligibility Criteria: Patients with HIV, Hepatitis B Virus, or Hepatitis C Virus Infections, Guidance for Industry 2020](#)). The following text was added: “Risk of HBV reactivation should be considered in all patients and the need for anti-HBV prophylaxis should be carefully assessed. Patients with chronic HBV infection with history of active disease who meet the criteria for anti HBV therapy should be on a suppressive antiviral therapy to be eligible for enrollment. Patients who are HCV Ab positive but HCV RNA negative due to prior treatment or natural resolution are eligible. Patients on concurrent HCV treatment at the time of enrollment are allowed if HCV RNA negative.”
- Sections [5.6](#), [5.6.1](#), [5.7.2](#), [8.2](#), [8.2.2](#), [Table 1](#) footnotes 15, 16; [Table 4](#): To conform language, “drug-related” was removed as a descriptor of AEs and replaced with “AEs for which relationship to THE-630 cannot be ruled out.”
- Section [8.2.2](#): Text was amended to make the AE causality definition of “related” more explicitly consistent with the definition of a DLT. The text was updated to clarify that a causality of “related” should be assigned for all AEs for which a relationship to THE-630 cannot be clearly and incontrovertibly ruled out.
- Sections [5.8.1](#), [6.3.10](#): Removed text related to the option of continued treatment despite objective progression if the patient is continuing to experience clinical benefit in the opinion of the Investigator.
- Synopsis was updated to reflect all applicable changes.

2.0	26-OCT-2023	Multiple	The follow populations, subgroups, endpoints and/or displays were dropped due to the reduction in scope for the terminated study (eg, removal of Prior SACT subgroup analyses, reduction in number of analysis sets, and descriptions of response): 
 -Response-Evaluable Analysis Set - Prior SACT Subgroup - Best Overall Response (BOR) and ORR, Confirmed and unconfirmed - Duration of Response (DOR), Confirmed responders-displays - Displays: - Table and/or figures referencing above were dropped or amended not to reflect said data. - OS: Table display - Labs: Table display (e.g., descriptive summaries, CTCAE grade increases) - Tissue/Blood Samples: All displays - Figures: labs, vital signs, and Spider Plots
3.0			Reduction in the number of TFLs required (the following displays/endpoints are dropped): 
 -All listings except for listings referenced as a table. -PFS, OS and time to response -Vital Signs/ECG/ Prior/Concomitant medications (e.g., Descriptive summaries) -several AE displays by preferred term

QMD Ref: CCI	Governing QMD: CCI
Confidentiality Statement	
CCI	

CCI		Sponsor: Theseus Pharmaceuticals, Inc.	
CCI		Protocol Number: THE630-21-101	
STATISTICAL ANALYSIS PLAN. PHASE 2-3-4			

1 INTRODUCTION

This is a Phase 1/2, open-label, multicenter trial to evaluate the safety, pharmacokinetics, and antitumor activity of THE-630 in patients with advanced GIST. The plan was to conduct the study in two parts: a dose escalation phase (Phase 1) and a subsequent expansion phase (Phase 2).

Enrollment was stopped after 32 patients were enrolled in Phase 1. Phase 2 will not be initiated.

Due to the termination of this study, the scope of reporting has changed. This amendment documents the updates to planned analyses due to the reduction in scope of the study. All details regarding the original study objectives, planned statistical displays and analysis components are detailed in SAP version 1.0. In general, the analyses planned have remained consistent with those defined in SAP version 1.0, but the scope has been reduced due to the lack of an expansion phase, and shorter follow-up of the study.

2 STUDY OBJECTIVES

Below objectives are as defined in the protocol. However, due to the termination of the study, certain objectives (e.g., Phase 2) are no longer applicable.

2.1 Primary Objectives

The primary objectives for the study are as follows:

- Dose Escalation (Phase 1): To determine the safety profile of oral THE-630, including the DLTs, MTD, and RP2D
- Expansion Cohorts (Phase 2): To determine the antitumor activity of oral THE-630 in patients with advanced GIST

2.2 Secondary Objectives

The secondary objectives for the study are as follows:

- Dose Escalation (Phase 1):
 - To determine the PK profile of oral THE-630 and its active metabolite THE-973
 - To document preliminary evidence of antitumor activity of oral THE-630 in patients with advanced GIST
- Expansion Cohorts (Phase 2):

QMD Ref: CCI	Governing QMD: CCI
Confidentiality Statement	
CCI	

CCI			
CCI		Sponsor:	Theseus Pharmaceuticals, Inc.
		Protocol Number:	THE630-21-101
STATISTICAL ANALYSIS PLAN. PHASE 2-3-4			

- To evaluate the safety profile of oral THE-630
- To further characterize the PK profile of oral THE-630 and its active metabolite THE-973

2.3 Exploratory Objectives

The exploratory objective for both phase 1 and phase 2 of the study is as follows:

- To explore associations between tumor and plasma biomarkers and THE-630 efficacy and safety

3 ENDPOINTS

3.1 Primary Endpoint

3.1.1 Phase 1

The primary endpoint of the dose escalation phase of the study is the safety profile of THE-630, including identification of DLTs and MTD, and determination of the RP2D.

3.2 Secondary Endpoints

3.2.1 Phase 1

Secondary endpoints of the dose escalation phase include:

- Plasma PK parameters of THE-630 and its active metabolite THE-973 after single oral dose and at steady state after multiple oral doses
- Efficacy assessments, according to modified RECIST 1.1 for patients with GIST including: confirmed objective response rate (ORR), best overall response, best target lesion response, time to response, disease control rate (DCR), Clinical Benefit Rate (CBR) at 16 weeks, PFS and OS

4 PLANNED ANALYSES

4.1 Analysis Sets

QMD Ref: CCI	Governing QMD: CCI
Confidentiality Statement	
CCI	

CCI			
CCI		Sponsor:	Theseus Pharmaceuticals, Inc.
		Protocol Number:	THE630-21-101
STATISTICAL ANALYSIS PLAN. PHASE 2-3-4			

4.1.1 Screened Set

The Screened Set includes all patients who signed informed consent and were allocated a patient number.

4.1.2 Enrolled Set

The Enrolled Set includes all screened set patients who meet eligibility criteria.

4.1.3 Full Analysis Set

The Full Analysis Set (FAS) includes all enrolled patients who receive at least one dose of THE-630. Unless otherwise stated, all primary efficacy and safety analyses will be conducted on the Full Analysis Set.

4.1.4 DLT-evaluable Analysis Set (phase 1 only)

The DLT-evaluable Analysis Set (Phase 1 only) will include patients enrolled in the Phase 1 dose escalation portion who completed at least 75% of the planned total dose during Cycle 1 (DLT evaluation period, i.e. 21 of 28 days) and patients who have experienced a protocol-defined DLT, regardless of dosing adherence in Cycle 1. Patients who do not receive study drug for at least 21 of 28 days (at least 75% of planned doses; not necessarily consecutively) during the first cycle for reasons not considered to be a DLT will be excluded from the DLT-evaluable Analysis Set. Additionally, patients who were enrolled as backfill enrollment will be excluded from the DLT-evaluable Analysis Set.

4.2 Derived Data

This section describes the derivations required for statistical analysis. Unless otherwise stated, variables derived in the source data will not be re-calculated.

4.2.1 Age

Age is defined as the age in years at time of informed consent as collected in the CRF.

The follow age groups (categorical) will be created for summary purposes:

Age group 1 (years): 18-64, ≥ 65

Age Group 2 (years): 18-49, 50-64, 65-74, ≥ 75 .

QMD Ref: CCI	Governing QMD: CCI
Confidentiality Statement	
CCI	
REF: CCI	Page 9 of 45

CCI			
CCI		Sponsor:	Theseus Pharmaceuticals, Inc.
		Protocol Number:	THE630-21-101
STATISTICAL ANALYSIS PLAN. PHASE 2-3-4			

4.2.2 Baseline

Baseline is defined as the last non-missing value (either scheduled, unscheduled or repeat) collected prior to first dose date and time of study drug for a given patient.

4.2.3 Duration / Study Day / Time

Study day will be calculated as the number of days from first dose of study drug.

- date of event – date of first dose of study drug + 1, for events on or after first dose
- date of event – date of first dose of study drug, for events before first dose

4.2.4 Prior Systemic Anticancer Therapy (SACT)

Prior TKIs (tyrosine kinase inhibitor) will be identified programmatically and through manual review of the data by the sponsor on an on-going basis. Final identification will be approved by the Sponsor before database lock. Additionally, for reporting purposes, prior SACTs that have different versions (e.g., salt vs no salt) and hence coded to different codes but will be considered the same SACT. These will be identified programmatically and through a manual review by the sponsor. Final identification will be approved by the Sponsor before database lock.

4.2.5 Conventions for Missing and Partial Dates

All rules explained below for partial / missing dates will be followed unless contradicted by any other data recorded on the electronic Case Report Form (eCRF).

All dates presented in the individual patient listings will be as recorded on the eCRF (i.e., not completed as per the below rules).

4.2.6 Missing / Partial Start / Stop Date of Adverse Events (AE) and Concomitant Medications

Missing and partial start and stop date will be imputed for analysis purposes as follows.

Partial or missing stop date will be imputed as follows:

If the stop date is completely missing and the event has resolved, or the patient has stopped taking the concomitant medication, the stop date will be imputed as the date of the patient’s last clinic visit in the study.

- If only the year is known, the stop date will be imputed as “31-Dec” of that year or as the date of the patient’s last clinic visit in the study if in the same year.

QMD Ref: CCI	Governing QMD: CCI
Confidentiality Statement	
CCI	

CCI			
CCI		Sponsor:	Theseus Pharmaceuticals, Inc.
		Protocol Number:	THE630-21-101
STATISTICAL ANALYSIS PLAN. PHASE 2-3-4			

- If the month and year are known, the stop date will be imputed as the last day of that month unless the stop date corresponds to the same month as the patient’s last clinic visit in which case the date of patient’s last clinic visit in the study will be used instead.

Missing start date will be imputed as follows:

- If the stop date occurs on or after the start of study drug or the event / concomitant medication is ongoing, the start date will be imputed as the date of the first dose of study drug.
- If the stop date occurs before the start of study drug, the start date of the event / concomitant medication will be imputed as the patient’s screening date or the stop date of the event / concomitant medication whichever the earlier.

Partial start date (year present, but month and day missing)

- If the stop date occurs on or after the start of study drug or the event / concomitant medication is ongoing, and the year is the same as the year of first dosing the start date will be imputed as “01-Jan” of the same year or the date of the first dose of study drug whichever is latest. If the year is different from the year of first dosing “01-Jan” will be used.
- If the stop date occurs before the start of study drug,
 - the start date of the concomitant medication will be imputed as the “01-Jan” of the same year.
 - the start date of the event will be imputed as the “01-Jan” of the same year or patient’s screening date, whichever is latest.

Partial start date (month and year present, but day missing)

- If the stop date occurs on or after the start of study drug or the event / concomitant medication is ongoing, the start date will be imputed as the first day of the same month and year unless this partial start date is in same month as the first dose of study drug in which case the date of first dose of study drug will be used.
- If the stop date occurs before the start of study drug, the start date will be imputed as the first day of the month and year of the partial stop date unless this partial start date is same month as patient’s screening visit in which case the date of screening will be used.

4.2.7 Missing Last Dates of Study Drug Dosing

If the date of last dose of study drug is completely missing, then the date of last dose of study drug will be taken for analysis purposes as the date of patient’s last clinic visit in the study or has been

QMD Ref: CCI	Governing QMD: CCI
Confidentiality Statement	
CCI	

CCI		Sponsor: Theseus Pharmaceuticals, Inc.	
CCI		Protocol Number: THE630-21-101	
STATISTICAL ANALYSIS PLAN. PHASE 2-3-4			

indicated to have discontinued treatment or has died whichever is earlier but no earlier than the date of first dose.

If only the month and year of the last dose was recorded, then the date of last dosing will be taken for analysis purposes as, the last day of the month of the recorded last dose or the date of patient's last clinic visit in the study or has been indicated to have discontinued treatment or has died whichever is earlier but no earlier than date of first dose.

4.2.8 Missing Diagnosis Dates

If the month and year are present but the day is missing, the diagnosis date will be set to first day of the relevant month. If only the year is recorded the diagnosis date will be set as "01-Jan" for that year.

4.2.9 Inexact Values

In the case where a variable is recorded as "> x", "≥ x", "< x" or "≤ x", a value of x will be taken for analysis purposes.

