4.15.2 Laboratory Data

QMD Ref: CCI	Governing QMD: CCI
Confidentiality Statement	
CCI	

CCI		Sponsor: Theseus Pharmaceuticals, Inc.	
CCI		Protocol Number: THE630-21-101	
STATISTICAL ANALYSIS PLAN. PHASE 2-3-4			

Laboratory samples will be analyzed by local laboratories. For reporting purposes, lab parameters will be reported using SI units.

Each measurement (continuous data) will be classed as below, within, or above normal range, based on ranges supplied by the laboratory used. To identify laboratory values of potential clinical importance, National Cancer Institute Common Terminology Criteria for Adverse Events (CTCAE) will be used to assign grades for select laboratory parameters where applicable (See [Appendix 4](#)). A shift table representing two-way frequency tabulation for baseline and the worst post-baseline value according to the CTCAE grade, by cohort and overall, will be provided. For analysis purpose, patients with a lab parameter value that does not meet CTCAE criteria (e.g., value is within normal range) at baseline or any time post-baseline, will be assigned a Grade of 0 for said visit.

The incidence of patients meeting Hy’s law criteria will be summarized for any time, post-baseline (See [Appendix 5](#)).

A listing of any abnormal laboratory measurements recorded throughout the study will be presented.

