12 APPENDIX 4: LABORATORY TESTS

12.1 Select Laboratory Parameters-CTCAE Grades

The following lab parameters will have CTCAE grades assigned based on numeric criteria listed for CTCAE v5.0 or v4.03. It should be noted that several parameters may have different set of grades based on the CTCAE term of interest (e.g., Sodium (decreased [CTCAE term: hyponatremia] and increased [CTCAE term: hypernatremia]), These CTCAE terms will be summarized separately.

Grades will be derived based on numeric criteria listed in CTCAE v5.0 (or v4.03 in cases where categorization for a laboratory assessment based on numerical value was not possible using CTCAE v5.0) and will not take into consideration clinical signs or symptoms. The below table lists numeric criteria used to determine a grade for a given a parameter value in this study. Note, a semi-colon indicates ‘or’ within the description of the grade.

Hematology

Parameter	CTCAE Term	Directionality	Grade 1	Grade 2	Grade 3	Grade 4
Hemoglobin	Anemia	Decrease	Hemoglobin(Hgb) <LLN-10.0 g/dL; <LLN-6.2 mmol/L; <LLN-100 g/L	Hgb <10.0-8.0 g/dL; <6.2-4.9 mmol/L; <100-80g/L	Hgb <8.0 g/dL; <4.9 mmol/L; <80g/L	N/A
White Blood Cells (WBC)	White Blood Cell Decreased	Decrease	<LLN-3000/mm3; <LLN-3.0 x 10e9/L	<3000-2000/mm3; <3.0-2.0 x 10e9/L	<2000-1000/mm3; <2.0-1.0 x 10e9/L	<1000/mm3; <1.0 x 10e9/L

QMD Ref: CCI	Governing QMD: CCI
Confidentiality Statement	
CCI	

CCI		Sponsor: Theseus Pharmaceuticals, Inc.	
CCI		Protocol Number: THE630-21-101	
STATISTICAL ANALYSIS PLAN. PHASE 2-3-4			

Parameter	CTCAE Term	Directionality	Grade 1	Grade 2	Grade 3	Grade 4
Platelet count	Platelet Count Decreased	Decrease	<LLN-75,000/mm ³ ; <LLN-75.0 x 10 ⁹ /L	<75,000-50,000/mm ³ ; <75.0-50.0 x 10 ⁹ /L	<50,000-25,000/mm ³ ; <50.0-25.0 x 10 ⁹ /L	<25,000/mm ³ ; <25.0 x 10 ⁹ /L
Neutrophil count (absolute)	Neutrophil Count Decreased	Decrease	<LLN-1500/mm ³ ; <LLN-1.5 x 10 ⁹ /L	<1500-1000/mm ³ ; <1.5-1.0 x 10 ⁹ /L	<1000-500/mm ³ ; <1.0-0.5 x 10 ⁹ /L	<500/mm ³ ; <0.5 x 10 ⁹ /L
Lymphocyte count (absolute)	Lymphocyte Count Decreased	Decrease	<LLN - 800/mm ³ ; <LLN - 0.8 x 10 ⁹ /L	<800 - 500/mm ³ ; <0.8 - 0.5 x 10 ⁹ /L	<500 - 200/mm ³ ; <0.5 - 0.2 x 10 ⁹ /L	<200/mm ³ ; <0.2 x 10 ⁹ /L

ULN=Upper limit of normal

Values in table are based on CTCAE v5.0.

Chemistry

Parameter	CTCAE Term	Directionality	Grade 1	Grade 2	Grade 3	Grade 4
Sodium	Hyponatremia	Decrease	<LLN-130 mmol/L	125-129 mmol/L	120-124 mmol/L	<120 mmol/L

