Sodium	Hypernatremia	Increase	>ULN-150 mmol/L	>150-155 mmol/L	>155-160 mmol/L	>160 mmol/L

QMD Ref: CCI	Governing QMD: CCI
Confidentiality Statement	
CCI	

CCI		Sponsor: Theseus Pharmaceuticals, Inc.	
CCI		Protocol Number: THE630-21-101	
STATISTICAL ANALYSIS PLAN. PHASE 2-3-4			

Parameter	CTCAE Term	Directionality	Grade 1	Grade 2	Grade 3	Grade 4
Potassium	Hypokalemia	Decrease	<LLN-3.0 mmol/L	N/A (for purpose of this study)	<3.0-2.5 mmol/L	<2.5 mmol/L
Magnesium	Hypomagnesemia	Decrease	<LLN-1.2 mg/dL; <LLN-0.5 mmol/L	<1.2-0.9 mg/dL; <0.5-0.4 mmol/L	<0.9-0.7 mg/dL; <0.4-0.3 mmol/L	<0.7 mg/dL; <0.3 mmol/L
Magnesium	Hypermagnesemia	Increase	>ULN-3.0 mg/dL; >ULN-1.23 mmol/L	>3.0-8.0 mg/dL; >1.23-3.30 mmol/L	>8.0 mg/dL; >3.30 mmol/L	N/A
Phosphorous (based on CTCAE v4.03 criteria)	Hypophosphatemia	Decrease	<LLN - 2.5 mg/dL; <LLN - 0.8 mmol/L	<2.5 - 2.0 mg/dL; <0.8 - 0.6 mmol/L	<2.0 - 1.0 mg/dL; <0.6 - 0.3 mmol/L	<1.0 mg/dL; <0.3 mmol/L
Calcium (Total) (correct calcium numeric criteria will be applied)	Hypocalcemia	Decrease	Corrected serum calcium of <LLN-8.0 mg/dL; <LLN-2.0 mmol/L	Corrected serum calcium of <8.0-7.0 mg/dL; <2.0-1.75 mmol/L	Corrected serum calcium of <7.0-6.0 mg/dL; <1.75-1.5 mmol/L	Corrected serum calcium of <6.0 mg/dL; <1.5 mmol/L

QMD Ref: CCI	Governing QMD: CCI
Confidentiality Statement	
CCI	

CCI		Sponsor: Theseus Pharmaceuticals, Inc.	
CCI		Protocol Number: THE630-21-101	
STATISTICAL ANALYSIS PLAN. PHASE 2-3-4			

Parameter	CTCAE Term	Directionality	Grade 1	Grade 2	Grade 3	Grade 4
Calcium Total (correct calcium numeric criteria will be applied)	Hypercalcemia	Increase	Corrected serum calcium of >ULN-11.5 mg/dL; >ULN-2.9 mmol/L	Corrected serum calcium of >11.5-12.5 mg/dL; >2.9-3.1 mmol/L	Corrected serum calcium of >12.5-13.5 mg/dL; >3.1-3.4 mmol/L	Corrected serum calcium of >13.5 mg/dL; >3.4 mmol/L
ALT	Alanine Aminotransferase Increased	Increase	>ULN-3.0 x ULN if baseline was normal; 1.5-3.0 x baseline if baseline was high abnormal (> ULN)	>3.0-5.0 x ULN if baseline was normal; >3.0-5.0 x baseline if baseline was high abnormal (> ULN)	>5.0-20.0 x ULN if baseline was normal; >5.0-20.0 x baseline if baseline was high abnormal (> ULN)	>20.0 x ULN if baseline was normal; >20.0 x baseline if baseline was high abnormal (> ULN)

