Alkaline phosphatase	Alkaline Phosphatase increased	Increase	>ULN-2.5xULN if baseline was normal; 2.0-2.5x baseline if baseline was high abnormal (i.e., > ULN)	>2.5-5.0xULN if baseline was normal; >2.5-5.0x baseline if baseline was high abnormal (i.e., > ULN)	>5.0-20.0xULN if baseline was normal; >5.0-20.0x baseline if baseline was high abnormal (i.e., > ULN)	>20.0xULN if baseline was normal; >20.0x baseline if baseline was high abnormal (i.e., > ULN)
Glucose (based on CTCAE v4.03 criteria)	Hyperglycemia	Increase	glucose value >ULN - 160 mg/dL; glucose value >ULN - 8.9 mmol/L	glucose value >160 - 250 mg/dL; glucose value >8.9 - 13.9 mmol/L	>250 - 500 mg/dL; >13.9 - 27.8 mmol/L	>500 mg/dL; >27.8 mmol/L
Glucose	Hypoglycemia	Decrease	<LLN-55 mg/dL; <LLN-3.0 mmol/L	<55-40 mg/dL; <3.0-2.2 mmol/L	<40-30 mg/dL; <2.2-1.7 mmol/L	<30 mg/dL; <1.7 mmol/L

QMD Ref: CCI	Governing QMD: CCI
Confidentiality Statement	
CCI	

CCI		CCI	
CCI		Sponsor:	Theseus Pharmaceuticals, Inc.
		Protocol Number:	THE630-21-101
STATISTICAL ANALYSIS PLAN. PHASE 2-3-4			

QMD Ref: CCI	Governing QMD: CCI
Confidentiality Statement	
CCI	

REF: CCI

CCI		Sponsor: Theseus Pharmaceuticals, Inc.	
CCI		Protocol Number: THE630-21-101	
STATISTICAL ANALYSIS PLAN. PHASE 2-3-4			

Coagulation

Parameter	CTCAE Term	Directionality	Grade 1	Grade 2	Grade 3	Grade 4
INR	INR Increased	Increase	>1.2-1.5; >1-1.5 x baseline if on anticoagulation**	>1.5-2.5; >1.5-2.5 x baseline if on anticoagulation**	>2.5; >2.5 x baseline if on anticoagulation**	
aPTT	Activated Partial Thromboplastin time prolonged	Increase	>ULN-1.5 x ULN	>1.5-2.5 x ULN	>2.5 x ULN	

**A subject who is taking a medication assigned WHODrug ATC3 level code “B01A” (antithrombotic agents) will be considered to be on an anticoagulation.

QMD Ref: CCI	Governing QMD: CCI
Confidentiality Statement	
CCI	

CCI			
CCI		Sponsor:	Theseus Pharmaceuticals, Inc.
		Protocol Number:	THE630-21-101
STATISTICAL ANALYSIS PLAN. PHASE 2-3-4			

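### Setting `<x` and `>x` to x under-grades a laboratory result whose reporting limit falls exactly on a CTCAE or strict Hy's law cut-off

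*SAP*

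**What the plan says.** SAP 4.2.9 covers all four inexact forms (`>x`, `≥x`, `<x`, `≤x`) with one instruction, "a value of x will be taken for analysis purposes", and makes no exception for data that are later categorised.

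SAP 12.1 (Appendix 4) assigns laboratory grades by program: "Grades will be derived based on numeric criteria listed in CTCAE v5.0", or v4.03 where needed. In its tables the boundary value sits in the milder grade. For WBC, Grade 3 is "<2000-1000/mm3; <2.0-1.0 x 10e9/L" and Grade 4 is "<1000/mm3; <1.0 x 10e9/L", so exactly 1.0 is Grade 3. Parameters graded upwards follow the same pattern: Grade 4 hyperglycemia is ">500 mg/dL; >27.8 mmol/L", so exactly 500 mg/dL is Grade 3. For hypokalemia, Grade 2 is "N/A (for purpose of this study", so the scale goes from Grade 1 (down to 3.0 mmol/L) straight to Grade 3 (below 3.0).

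SAP 4.15.2 uses the grades in shift tables of "baseline and the worst post-baseline value according to the CTCAE grade". It also counts patients who meet the Hy's law criteria of Appendix 5. On the source of the data it says "Laboratory samples will be analyzed by local laboratories".

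**The concern.** A strict inequality recorded by the laboratory is information. A WBC of `<1.0` x 10e9/L is Grade 4 by the SAP's own definition, whatever the true value. Replacing it with 1.0 discards the sign, and the program returns Grade 3. Nothing later in the SAP restores the sign.

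Replacing a censored value with x is a reasonable convention for means and medians. The laboratory outputs that remain in SAP 4.15.2 are the shift tables, the Hy's law summary and a listing of abnormal values. For laboratory data the rule therefore now works mainly through categories, where it can give a wrong answer. The listing could show `<1.0` for a patient whom the shift table places in Grade 3.

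**Working it through.** The SAP gives no figure to reproduce, so the check applies the 4.2.9 rule to each Appendix 4 cut-off.

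**Inputs.** The fixed-number and ULN-multiple cut-offs in SAP 12.1: 12 parameters graded downwards with 33 cut-offs, and 14 graded upwards with 40. That is 26 parameter-direction combinations and 33 + 40 = 73 cut-offs. Grade 1 limits set at LLN or ULN, and grades defined as multiples of baseline, are left out. LLN is assumed to lie above the first downward cut-off, and ULN below the first upward one. Hyponatremia Grades 2 and 3 are printed as integer bands and are read as boundaries at 130, 125 and 120 mmol/L.

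**Method.** For each cut-off c, take a report of `<c` (downward) or `>c` (upward). Compare
- the grade under 4.2.9, g(c), with
- the mildest grade consistent with the report, which is g just below c or just above c.

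**Reporting limit equal to a cut-off.** The rule under-grades at 73 of 73: by one grade at 72 and by two at 1.

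| Recorded result | Value used | Grade under 4.2.9 | Mildest grade consistent with the record |
|---|---|---|---|
| WBC `<1.0` x 10e9/L | 1.0 | 3 | 4 |
| Platelets `<25` x 10e9/L | 25 | 3 | 4 |
| Neutrophils `<0.5` x 10e9/L | 0.5 | 3 | 4 |
| Glucose `>27.8` mmol/L | 27.8 | 3 | 4 |
| Lipase `>5` x ULN | 5 x ULN | 3 | 4 |
| INR `>1.2` (no anticoagulation) | 1.2 | 0 | 1 |
| Potassium `<3.0` mmol/L | 3.0 | 1 | 3 |

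Potassium loses two grades because Grade 2 is not used.

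**Reporting limit off a cut-off.** Neutrophils `<0.1` and platelets `<10` are past the last cut-off and are correctly Grade 4. Platelets `<30` become Grade 3 when the truth is 3 or 4; lipase `>3` x ULN likewise. Those grades may be too mild but are not known to be wrong.

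**Hy's law (Appendix 5).** Total bilirubin recorded as `>2` x ULN becomes 2 x ULN and fails the strict `>2` x ULN criterion. INR `>1.5` becomes 1.5 and fails `>1.5`. ALT or AST `>3` x ULN becomes 3 x ULN and fails that part of both joint criteria. The ALT and AST bands use `≥`, so a `>` report on a lower edge is still counted. The second joint criterion uses `≥2` x ULN for bilirubin, so that component survives the substitution.

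**Size in a table.** Tables 14.3.4.2 to 14.3.4.4 use the Full Analysis Set. If all 32 enrolled patients were dosed, one misgraded patient is 1/32 = 3.1% of the overall column. In a cohort at the protocol's minimum of three it would be 1/3 = 33%. The cell changes only if the affected result sets the patient's baseline grade or worst post-baseline grade.

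**After the fix.** If `<x` is graded as just below x and `>x` as just above x, all 73 cut-offs return the mildest grade consistent with the record.

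**The case against.** The strongest case against is that this may never occur. The error is certain only when a laboratory's reporting limit coincides with a CTCAE or Hy's law cut-off. The documents give no reporting limits, and nothing in them suggests that any laboratory reports this way. The study is terminated and its analyses are descriptive. Abnormal values are listed in Table 14.3.4.1. This limits the importance of the point, but the stated rule still gives a wrong grade when the coincidence arises.

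A reader might infer several stronger things that the documents do not support:

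- *That every result beyond a reporting limit is under-graded.* Neutrophils `<0.1` show otherwise.
- *That DLT or MTD findings are biased.* SAP 4.2.13.2 takes DLTs from reported adverse events flagged in the database. Protocol 8.2.1 has AE severity graded by CTCAE for the AE record, separately from the derived laboratory grades.
- *That toxicity is always understated.* This holds for the fixed and ULN-multiple cut-offs. However, ALT, AST, bilirubin and alkaline phosphatase are graded as multiples of baseline when baseline is above ULN. A baseline recorded as `>x` and set to x makes the denominator too small, so a later grade can be too high. An under-graded baseline also exaggerates a shift.
- *That each table row rests on 3 to 6 patients.* That is the escalation cohort size. The Full Analysis Set includes backfill patients, whom the protocol allows at up to 20 per dose level. The cohort sizes actually reached are not stated.

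**Conclusion.** The point stands as a minor, correctable error in a stated rule. Where a recorded limit equals a strict cut-off, in the unit used for grading, SAP 4.2.9 and Appendix 4 together assign a grade that the record itself contradicts: one grade too mild in most cases, and two for potassium `<3.0` mmol/L. The strict Hy's law criteria can miss a patient in the same way. The reach is limited to Tables 14.3.4.2 to 14.3.4.4 and the strict Hy's law counts. The number of affected results cannot be estimated from the documents; it ranges from none to every result whose limit falls on a cut-off.

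**What to change.** Add one sentence to SAP 4.2.9: for CTCAE grading and threshold flags the recorded inequality sign is used, so `<x` counts as strictly below x and `>x` as strictly above x, with the value taken to lie immediately beyond x. For a report in the direction of worsening, this gives the mildest grade consistent with the record. Keep x for `≤x` and `≥x`, for descriptive statistics, and for baseline values used as denominators.

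The shift should be infinitesimal, not one unit of the last reported digit. With coarse reporting, a one-unit shift turns magnesium `<1` mg/dL into 0, which is Grade 4, although a true 0.9 is Grade 2. It turns INR `>2` into 3, which is Grade 3, although 2.1 is Grade 2. The sign should also be carried through the conversion to SI units in SAP 4.15.2.

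The cost is one sentence and a small code change. A search of the laboratory data for inexact results on a cut-off would show whether any table cell changes.
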